- k For subjects who receive non-trial SARS-CoV-2 vaccinations there will be no sampling in subsequent visits. Information about these vaccinations may be received outside of a planned visit and can be collected remotely, e.g., by phone. In such cases information on physical examination and vital signs can be skipped. However, AEs that occurred prior to administration of non-trial vaccine must be enquired and should be recorded as stated in footnote "i".
- Record any non-trial SARS-CoV-2 vaccinations that trial subjects receive during the trial in the CRF until the last trial visit.

Abbreviations: AE = adverse event; AESI = adverse event of special interest; CMI = cell mediated immunity; CRF = case report form; d = day; ELISA = enzyme-linked immunosorbent assay; EOT = end of trial; h = hour(s); IMP = investigational medicinal product; inj. = (IMP) injection; NAAT = nucleic acid amplification-based test; NATAB = neutralizing antibody titers and antibody binding; SAE = serious adverse event; SARS-CoV-2 = the virus leading to COVID-19; SoA = schedule of activities; WOCBP = women of childbearing potential.

		Page 12
BioNTech SE	Clinical Trial Protocol	Versio
Confidential	BNIT162 14	VEISIO
Connuential	DINT 102-14	Dete: 00 I

Page 12 of 91 Version: 4.0 Date: 20 JAN 2022

Table 2: Schedule of events for Immunology Subgroup of Group B (with two injections of Comirnaty) h

Activity	Visit 0	Visit 1	Visit 2	Visit 3	Visit 4	Visit 5	Visit 6 ^{I, m}	Visit 7 ^{I, m, o}	Early termination
Week(s)			1	3	4	7	12	26	
Day	-30 to -1	1	8+2	22±3	29+7	50±7	85±10	182±20	
	(Screening)	(Day of inj. 1; pre-dose except IMP injection)	(~7 d post inj. 1)	(~21 d post inj. 1; pre-dose except IMP injection)	(~7 d post inj. 2)	(~28 d post inj. 2)	(~63 d post inj. 2)	(~161 d post inj. 2 EOT Visit)	
Collect informed consent	Х						X m	X m	
Assess inclusion/exclusion criteria compliance	Х	X (review)							
Collect demographic and medical history	Х	X (update)							
Physical examination	Х	X a	X a	X a	X a			X a	X a
Vital signs, body weight ^b	Х	Хc		Хc					
Urine pregnancy test for WOCBP	Х	х		х				х	х
Blood draw for clinical laboratory (15 mL) ^d	Х								
Allocation to IMP		х							
IMP injection, then observe subjects for ~1 h		х		X ^h					
Subject hotline availability	Start	=>	=>	=>	=>	=>	=>	End	(End)
Oral swabs for NAAT-based SARS-CoV-2 for screening ^f	X e	X e							
Oral swab for NAAT-based SARS-CoV-2 testing for surveillance			х	x	х	Х	х	х	x

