3 OBJECTIVES AND ENDPOINTS

OBJECTIVES	ENDPOINTS	
Primary objectives	Endpoints	
To determine the safety and tolerability of one or two boosting doses of Comirnaty or one dose of BNT162b2s01 in BNT162-01 trial subjects, or two boosting doses of Comirnaty in BNT162-04 trial subjects.	 For all Group A and Group B subjects: The proportion of subjects in each treatment group with at least one SAE or the proportion of AESIs occurring up to 26 weeks after the first IMP injection. For Group A and a selected subset of Group B subjects: The frequency of solicited local reactions (pain, tenderness, erythema/redness, induration/swelling) at the injection site recorded up to 7 d after each IMP injection. The frequency of solicited systemic reactions (vomiting, diarrhea, headache, fatigue/tiredness, fever, chills, nausea, new or worsened muscle pain, new or worsening joint pain) recorded up to 7 d after each IMP injection. The proportion of subjects with at least one unsolicited TEAE occurring up to 28 d after IMP injection in each treatment group. 	
Secondary objectives	Endpoints	
To describe changes in SARS-CoV-2 neutralizing antibody titers from baseline to reference and SARS-CoV-2 variant B.1.351.	 For Group A and Group B subjects (except transplant subjects): Antibody titers to recombinant S1 and RBD protein derived from reference and SARS-CoV-2 variant B.1.351** will be assessed at baseline (Day 1) and then Day 8, Weeks 3*, 4, 7*, 12, and 26: Neutralizing antibody titers. Antibody titers (ELISA). SARS-CoV-2 functional cross-neutralization of variant B.1.351** to reference strain. *Group B only **Group B transplant subjects only: Antibody titers to recombinant S1 and RBD protein derived from SARS-CoV-2 will be assessed at baseline (Day 1) and then Day 8, Weeks 4, 12, and 26 post Dose 1, and at Dose 2 (Day 1) and then Day 8, Weeks 4, 12, and 26 post Dose 2: Neutralizing antibody titers. Antibody titers (ELISA). 	
Exploratory objectives	Endpoints	

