6 TRIAL TREATMENTS

Trial treatment is defined as any investigational treatment(s), marketed product(s), intended to be administered to a trial subject according to the trial protocol.

IMP name:	BNT162b2 (Comirnaty) or BNT162b2s01.
Туре:	Vaccine (BNT162 RNA-LNP vaccine utilizing modRNA).
Administration route:	Intramuscular (IM); upper arm, musculus deltoideus. The same arm may be used for both immunizations. The non-dominant arm is preferred.
Dosing regimen:	Group A: One (at Day 1) IM injection with 30 µg of either Comirnaty or BNT162b2s01.
	Group B: Two (at Day 1 and Day 21) IM injections with 30 μg of Comirnaty, except Group B transplant subjects.
	Group B transplant subjects: Two IM injections of 30 µg of Comirnaty, with injection 2 administered 3 to 7 months after injection 1 (Day 1).
	The planned time points for injection of IMP for Groups A and B are provided in the SoA (Section 1.3).
Sourcing:	Provided centrally by the sponsor.
Packaging and labeling:	IMP will be provided in glass vials as open-label supply. Each vial will be labeled as required per country requirements. For details, see the Pharmacy Manual.

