8.2.4 Subject diaries

For Group A and Group B Immunology Subgroup trial subjects, subject diaries will be issued and collected by trial site personnel at the visits given in the SoA (Section 1.3).

Trial subjects will be asked to record any solicited local reactions at the injection site (pain, tenderness, erythema/redness, induration/swelling), and solicited systemic reactions (vomiting, diarrhea, headache, fatigue/tiredness, fever [oral temperature of ≥38.0°C], chills, nausea, new or worsened muscle pain, new or worsening joint pain). Data will be recorded on the reactogenicity CRF, NOT on the AE CRF/log unless the reactogenicity AE extends past Day 8. If one of the solicited reactogenicity adverse events from the subject diary fulfills SAE criteria, additional CRF SAE data must be provided.

For Group B transplant subjects, a subject diary should be distributed when they receive their second vaccination.

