8.3 Adverse events and serious adverse events

The investigator and any qualified designees are responsible for detecting, documenting, and recording events that meet the definition of an AE or SAE or AESI and are responsible for following up all AEs and SAEs.

The detection of AE or SAE or AESI is unsolicited.

Solicited AEs that are recorded from the subject diaries on the reactogenicity CRFs should not be reported as AEs unless the solicited AE meets criteria for SAE or begins after Day 8 or started before Day 8 and continues past Day 8.

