9.4.2 Primary endpoints

The primary endpoints are defined in Section 3.

All AEs will be coded using the most recent version of Medical Dictionary for Regulatory Activities (MedDRA[®]) coding system to get a system organ class (SOC) and preferred term (PT) for each AE.

Reactogenicity

Solicited local and systemic reactions (from the subject diary) will be summarized using the Safety Set. In general, solicited reactions will be analyzed for each immunization, i.e.:

• Up to 7 d after each IMP injection

For each injection, the number and percentage of subjects reporting at least one local reaction or systemic reaction (i.e., solicited data collected using subject diaries) will be summarized for each of the following types using the Safety Set:

BioNTech SE	Clinical Trial Protocol
Confidential	BNT162-14

- Any local reactions or systemic reactions
- Grade ≥3 local reactions or systemic reactions

Moreover, the number and percentage of subjects reporting at least one local reaction will be summarized by worst grade using the Safety Set.

Unsolicited TEAEs

For Group A and Group B immunology subset, the number and percentage of subjects reporting at least one TEAE (defined in Section 10.3.1) will be summarized by PT nested within SOC for each of the following AE types using the Safety Set:

- Any AE
- Related AE
- Grade of AE
- Related Grade ≥3 AE
- Any solicited AE that continues past 7 d post-trial injection or is an SAE, or AE that fits the definition of a solicited AE but starts after Day 8
- Any SAE
- Related SAE
- AESI

Moreover, the number and percentage of subjects with any AE will be summarized by worst grade by PT nested within SOC.

For Group B, AESIs and SAEs will be analyzed.

Additional AE analyses may be described in the SAP.

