6.1.2. Definitions and derivations

Unscheduled visits

Unscheduled visits will not be included in the summary tables but will be included in the listings.

Variables

Unless otherwise specified, **baseline** is defined as last value prior to first injection of IMP (Dose 1) given in this BNT162-14 trial on Day 1, including unscheduled visits.

Change from baseline will be calculated as follows:

• Change from baseline = post-baseline assessment value – baseline assessment value.

Duration [days] will be calculated as follows:

• Duration [days] = last observation date – first observation date + 1

Time from first injection (Dose 1) to first reaction will be calculated as follows: Time from first injection to first reaction [days] = first reaction date – date of first injection (Dose 1) + 1

Time from first reaction to last reaction will be calculated as follows:

Time from first to last reaction [days] = last reaction date – first reaction date + 1

Days since last injection will be calculated as follows:

Days since last injection = onset date of AE – date of last injection +1

For conversion of days to months or years the following rules will be applied:

- 1 month = 30.25 days
- 1 year = 365.25 days

Study Day and are defined as follows:

- Study day:
 - If study date < date of first injection (Dose 1), then study day = study date date of first injection
 - If study date >= date of first injection (Dose 1), then study day = study date date of first injection + 1

Fold rise will be calculated as follows:

• Fold rise = post-dose value / baseline value

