6.4.3. Adverse events

Definition

For detailed information on adverse events see Section 10.3 of the protocol. Solicited AEs that are recorded from the subject diaries on the reactogenicity CRFs will not be reported as AEs unless the solicited AE meets criteria for SAE or begins after Day 8 or started before Day 8 and continues past Day 8.

Adverse events (AEs) will be coded using the Version MedDRA[®] 24.0 to get a system organ class (SOC) and preferred term (PT) for each AE.

A TEAE is defined as any AE with an onset after the first injection (Dose 1) (if the AE was absent before the first injection) or worsened after the first injection (Dose 1) (if the AE was present before the first injection (Dose 1)). AEs with an onset date more than 28 days after the last injection will be considered as treatment emergent only if

assessed as related to IMP by the investigator. AEs that cannot be determined to not be treatment emergent due to missing date or time will be defined as TEAE.

Note: To clarify the definition in the protocol, AEs with an onset date at the date of the first injection (Dose 1) will only be considered as treatment emergent if the AE occurred after the first injection (Dose 1). AEs with missing time and occurring on the day of Dose 1 or AEs with missing date will be analyzed as treatment emergent.

TEAEs will be evaluated for following time interval and groups:

- Up to 28 days after the first IMP injection (Group A and immunology subset of Group B)
- After the first IMP injection up to 28 days after the second IMP injection (immunology subset of Group B non-transplant)
- After the second IMP up to 28 days after the second IMP injection (immunology subset of Group B transplant)
- All TEAEs (Group A and immunology subset of Group B)

AEs are assigned to the time interval according to their start date and time. AEs with missing date will be assigned to each of the respective intervals if it cannot be ruled out, that it belongs to the time interval.

Adverse events of special interest (AESIs)

The following events will be reported as AESIs: myocarditis, pericarditis, anaphylaxis, thromboembolic events (e.g., deep vein thrombosis, stroke, myocardial infarction), immune thrombocytopenia and immune based neurologic events (e.g., optic neuropathy, Guillain-Barré syndrome). AESIs are recorded in the CRF.

AESIs and SAEs will be evaluated up to 26 weeks after the ICF was signed for all groups.

Analysis

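### The Day 8 cut-off between diary reactions and AEs is not tied to an injection, so Dose 2 reactions in 114 planned Group B subjects can enter the primary unsolicited-TEAE endpoint

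*Protocol*

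**What the plan says.** **The cut-off.** Protocol 8.3 excludes diary reactions from AE reporting "unless the solicited AE meets criteria for SAE or begins after Day 8 or started before Day 8 and continues past Day 8". SAP 6.4.3 carries the same test: "begins after Day 8 or started before Day 8 and continues past Day 8". Protocol 8.2.4 has a shorter version, under which diary data go on the reactogenicity form, "NOT on the AE CRF/log unless the reactogenicity AE extends past Day 8". Protocol 9.4.2 lists, among the unsolicited TEAE types, solicited events that are serious or that outlast seven days from the trial injection, and also any "AE that fits the definition of a solicited AE but starts after Day 8".

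**The day scale.** SAP 6.1.2 defines study day from Dose 1 only: "If study date >= date of first injection (Dose 1), then study day" is the date difference from that injection plus one. In Protocol Table 2 (Group B immunology subgroup), Day 8 is Visit 2 and injection 2 is at Visit 3, Day 22±3, labelled as about "21 d post inj. 1; pre-dose except IMP injection". The dosing table in Protocol 6 reads "Two (at Day 1 and Day 21) IM injections with 30" µg for non-transplant Group B. Transplant subjects receive injection 2 at 3 to 7 months, and Table 2a restarts its day count there.

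**The endpoint.** For Group A and the Group B subset, one primary endpoint is "The proportion of subjects with at least one unsolicited TEAE occurring up to 28 d after IMP injection in each treatment group". For the non-transplant subset, SAP 6.4.3 uses a TEAE interval that runs from the first injection to 28 days after the second. Solicited reactions up to 7 days after each injection are separate primary endpoints.

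**The concern.** A cut-off that sorts events into solicited and unsolicited has to restart at each injection. This one names a day without naming the injection, and the only day scales that apply to non-transplant Group B start at injection 1. Taken at its word, the rule works for Dose 1 and does nothing at Dose 2. Ordinary arm pain the day after injection 2 belongs in the diary and also qualifies as an AE, because it starts after Day 8.

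The SAP does not repair this downstream. Section 6.4.3 lists nine TEAE types and a separate table of solicited TEAEs by SOC and PT, but no row for unsolicited TEAEs and no statement that solicited events are removed from the row for any TEAE. A primary safety proportion could therefore largely restate Dose 2 reactogenicity. If some sites read Day 8 per injection and others from Dose 1, the proportion would also vary with site practice.

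**Working it through.** **1. Who is exposed.** Protocol 4.1 gives the immunology subset by cohort: 36 + 30 + 15 + 48 = 129, which matches the stated 129. Removing the 15 transplant subjects leaves 129 − 15 = 114, and 114/459 = 24.8% of the Group B maximum. The other 459 − 129 = 330 keep no diary (8.2.4), and only AESIs, SAEs and COVID-19-linked AEs are recorded for them (Table 3). Group A has one injection, so only the boundary-day question in step 5 concerns it.

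**2. Day arithmetic.** Injection 2 at Day 22±3 falls on Days 19 to 25. All of these are later than Day 8, as is the Day 21 in the dosing table, so the result does not depend on how those two entries are reconciled. On a Dose 1 scale, every Dose 2 reaction begins after Day 8. On a per-injection scale, Day 8 of Dose 2 is the injection day plus 7: study Day 29 for an injection on Day 22, and study Days 26 to 32 across the window.

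**3. Where the events land.** The Dose 2 diary week lies wholly inside the TEAE interval ending 28 days after injection 2, so events reported under the literal reading enter that interval.

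**4. Illustrative size.** The plan has no figure to reproduce, since it states no hypothesis and no sample-size calculation. Let *u* be the true proportion with an unsolicited TEAE and *r* the proportion with at least one Dose 2 solicited reaction. Treat the two as independent and assume every reaction is entered as an AE. Then

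reported proportion = 1 − (1 − u)(1 − r).

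| u | r = 50% | r = 80% | r = 90% |
|---|---|---|---|
| 10% | 55% | 82% | 91% |
| 20% | 60% | 84% | 92% |
| 30% | 65% | 86% | 93% |
| 40% | 70% | 88% | 94% |

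At u = 20% and r = 80%, the count among 114 goes from 22.8 to 95.8. In a total column that includes the 15 transplant subjects at rate u, the figure is (114 × 0.84 + 15 × 0.20)/129 = 76.6%. Without independence, the reported proportion still cannot be below the larger of u and r. On a per-injection reading, reactions confined to the Dose 2 week add nothing and the proportion stays at u.

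Both rates are assumptions. Protocol 2.3.1 cites injection-site pain above 80% after two doses, and again after a third dose, but from another trial and not for Dose 2 of this schedule. No unsolicited rate is given.

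**5. Onset exactly on Day 8.** The provisions compare as follows:

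- SAP 6.4.1 and 6.4.2: the solicited interval is study days 1 to 7, so Day 8 is outside it.
- Protocol Table 1: the diary covers Day 1 and the 7 days after, so Day 8 is inside it.
- Protocol 8.3 and SAP 6.4.3: Day 8 is neither before nor after Day 8, so the event is not assigned.
- Protocol 8.2.4: the event goes to the AE form only if it runs past Day 8.
- Protocol 9.4.2: the persistence limb catches it on the same condition.

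A short, non-serious reaction starting on Day 8 can therefore miss both primary endpoints.

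**The case against.** The best defence is that Day 8 is shorthand for seven days after an injection given on Day 1, and that the authors meant it to restart. There is good support for this. The solicited endpoints run to 7 days after each injection. SAP 6.4.1 gives Dose 2 its own interval and says the day 1 to 7 convention carries over. One limb of the 9.4.2 bullet measures persistence from the trial injection. Table 2 issues a fresh diary at injection 2, which would make little sense if every entry were also an AE. Table 2a restarts at Day 1 for transplant subjects. Nor does the rule use the SAP's defined term, study day. All of this stands as evidence of intent, and it makes inflation uncertain.

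It does not settle the text. Where a per-injection clock was wanted elsewhere, it was written out. The 9.4.2 bullet uses both clocks in one sentence, and Table 2, the schedule sites follow for these subjects, numbers Day 8 from injection 1.

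The separate solicited-TEAE table would make misallocated events visible, which also stands. Visibility is not removal, and the SAP does not define that category.

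A reader might infer that all Group B Dose 2 reactions are affected. They are not: 330 subjects have no diary or unsolicited-TEAE endpoint, and transplant subjects follow a renumbered schedule. A reader might also infer that a reaction starting on Day 8 can never become an AE. Protocol 8.2.4 catches it if it persists. Nor is a comparison with Group A at stake: none is planned, Group B is not randomised, and its TEAE interval is longer in any case.

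**Conclusion.** The concern holds as an internal contradiction with a material risk. The cut-off is unanchored in Protocol 8.2.4 and 8.3, in the late-onset limb of 9.4.2 and in SAP 6.4.3. Read with the applicable day scales, it sends every Dose 2 diary reaction in 114 planned subjects into the AE data, against the per-injection wording elsewhere. The SAP has no step that takes those events out of the unsolicited-TEAE endpoint.

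It would go too far to say that the endpoint will be inflated or to give a single inflated value. The 55% to 94% range rests on assumed rates, independence and full AE entry of diary reactions, and the per-injection reading gives no inflation. What the documents support is that one primary safety proportion depends on how each site reads two words. The boundary-day inconsistency is smaller, but it also touches Dose 1 and Group A.

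**What to change.** 1. In Protocol 8.2.4, 8.3 and 9.4.2 and SAP 6.4.3, count the cut-off from the most recent injection.
2. Assign the boundary day once, so that the SAP solicited interval and the AE rule meet without a gap. If the interval stays at days 1 to 7, late onset should mean Day 8 or later, counted from that injection. If Day 8 is treated as solicited, SAP 6.4.1 and 6.4.2 should extend to it.
3. Add to SAP 6.4.3 a row for unsolicited TEAEs and name it as the primary endpoint analysis. It should exclude solicited-term events with onset inside the 7-day window after any injection, unless they are serious or continue past that window. Those exceptions must stay, because 9.4.2 deliberately keeps such events; a blanket exclusion of solicited terms would drop them.
4. Derive the row from recorded onset and end dates, not from the form on which the event was entered. Dose 2 diary events already entered as AEs are then handled alike at all sites. This matters because Protocol 10.9.3 says no parent-trial subjects were left to roll over, so many entries may already exist.

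The cost is a few words in four places, a possible edit to the SAP solicited interval, and one derived flag. No new data are needed, since AE start and end dates are already collected (Protocol 10.3.1.7).

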8.3.1 Time period and frequency for collecting AE, AESI, and SAE information

For trial subjects enrolled in this clinical trial, i.e., after transfer from the parent trial to this trial, all AEs, AESI, and SAEs (including a death) will be recorded at the time points listed in the SoA in Section 1.3. All safety reporting will occur through this rollover trial; this includes the reporting of non-vaccine related AEs that are unresolved from the parent trial.

For subjects who receive a non-trial SARS-CoV-2 vaccination, AEs/SAEs will be collected as specified above until the date when the subject was vaccinated with the non-trial SARS-CoV-2 vaccine. The AEs expected to be captured after non-trial SARS-CoV-2 vaccination are within the frame of post-marketing safety data reporting.

Investigators are not obligated to actively seek AEs or SAEs at any time after a trial subject has been discharged from the trial, however, if the investigator learns of any SAE (including a death), that they consider to be reasonably related to the IMP administration or trial participation, the investigator must promptly notify the sponsor.

8.3.2 Method of detecting AEs and SAEs

The method of recording, evaluating, and assessing causality of AEs and SAEs and the procedures for completing and transmitting SAE reports are provided in Section 10.3.

Care will be taken not to introduce bias when detecting AEs or SAEs. Open-ended and non-leading verbal questioning of the trial subject is the preferred method to inquire about AE occurrences.

